5.5.4 Instructions for prescribing and taking study treatment

All kits of study treatment assigned by the IRT will be recorded/databased in the IRT.

ZPL389 will be provided as 3 mg, 10 mg, 30 mg and 50 mg powder in capsules. Placebo will be provided as visually matched capsules. Bottles of capsules will be dispensed at study visits occurring at Baseline and every 4 weeks thereafter. All study drugs will be supplied in identical bottles and will be the same color and appearance, thereby maintaining double-blind conditions.

Study medication will be supplied to the subject at:

- Baseline visit (Day 1): 1 bottle of ZPL389 or matching placebo
- Week 4 (Day 29): 1 bottle of ZPL389 or matching placebo
- Week 8 (Day 57): 1 bottle of ZPL389 or matching placebo

• Week 12 (Day 85): 1 bottle of ZPL389 or matching placebo

Note: Investigators must check the number of doses already taken by the subject, and ensure that the Week 16 visit is scheduled such that the subjects take approximately 112 capsules in total.

Subjects must be instructed to take one capsule per day at the same time every day preferably in the morning (e.g. every day at 8 am). The subject will record the intake of study medication on a daily basis on the subject e-diary. On days of a scheduled study visit, subjects must be instructed to:

- bring all current study medication with them to the visit
- not take the investigational treatment at home on the day of a study visit but must take it when instructed by study personnel at the investigational site

The investigator must promote compliance by instructing the subject to take the study treatment exactly as prescribed and by stating that compliance is necessary for the subject's safety and the validity of the study. The subject must also be instructed to contact the investigator if he/she is unable for any reason to take the study treatment as prescribed.

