
The concept of assessment windows will be used for the data that is summarized by visit. Each assessment window is based on the study evaluation schedule and comprises a set of days around the nominal visit day. For any assessment, there are the protocol defined scheduled visits around which windows were created to cover the complete range of days within the study. The visit windows are shown in Table 2-1.

These assessment windows apply to measurements taken at every visit. For assessments which are not collected at every visit, the assessment windows defined in Table 2-1 will be combined. For example, if an assessment is measured at Week 4 and Week 8 only, the Week 4 assessment window for this parameter will extend from Day 2 to Day 43 (combining Week 2 to Week 4), Week 8 will extend from Day 44 to Day 71 (combining Week 6 to Week 8).

When assessment windows are used, all visits will be re-aligned, i.e., they will be mapped into one of the assessment windows. For example, if the Week 4 visit of a subject is delayed and occurs on Day 60 instead of on Day 29, the data will be considered to relate to Week 8. In the case of major deviations from the visit schedule, or due to unscheduled visits, several assessments of a subject may fall in a particular assessment window (either scheduled or unscheduled). The approaches to handle multiple assessments in a given window are specified below.

Assignment of data to the assessment windows will be done before deriving further parameters (e.g. change from baseline, responder status) from the assessments. The assessment windows will be used for summary tables and figures but listings will show the original visit at which the data were recorded, along with the study day of the assessment.

I able 2-1			
Visit as used for reporting	Week	Scheduled study day	Assessment window
Screening	SCN	-35 to -1	Day -35 to -1
Baseline	0	1	Day 1
Week 2	2	15	Day 2 – 22
Week 4	4	29	Day 23 – 26
Week 6	6	43	Day 37 – 50
Week 8	8	57	Day 51 – 71
Week 12	12	85	Day 72 – 99
Week 16	16	113	Day 100 – 127
Week 20	20	141	Day 128 – 155
Week 28	28	197	Day 184-211
Week 32	32	225	Day 212-267
Week 44	44	309	Day 268-351
Week 56	56	393	Day 352-435
Week 68	68	477	Day 436-519
Week 80	80	561	Day 520-603
Week 92	92	645	Day 604-687

Table 2-1Visit windows

Novartis For business use only SAP		Page 15 CZPL389A2203	
Visit as used for reporting	Week	Scheduled study day	Assessment window
Week 104	104	729	Day 688-771
Week 116	116	8130	Day 772-827

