# 2.7.1 Adverse events (AEs)

Adverse events will be coded according to the MedDRA dictionary. The actual MedDRA version used for reporting the adverse events will be described in a footnote of the CSR tables.

Only treatment emergent AEs will be presented. Treatment emergent adverse events are those events that

- started after the first dose of study treatment, or
- were present prior to the first dose of study treatment but increased in severity based on preferred term.

AEs observed four weeks or more after last study treatment intake will not be considered as treatment-emergent.

The purpose of the AE summaries are to understand what AEs are reported within different time periods relative to start of treatment. Thus AEs will be summarized for different time periods to cover the core and extension studies. Since AEs reported in a period may also be affected by AEs in any previous periods of treatment, the treatment groups for periods after 16 weeks will separate subjects who received placebo and the lower ZPL389 doses for the first 16 weeks of their treatment from those who had already received 30mg or 50mg ZPL389 for 16 weeks.

Therefore AEs will be summarized across the following time periods

- AEs with onset date during the first 16 weeks of treatment where treatment group is the treatment group in the core study. This summary will be based on the full safety set.
- AEs with onset date after week 16 but before week 32 of study treatment. This summary will be based on the subset of the safety set comprised of patients who have on study treatment data after week 16. Treatment groups for this summary are
  - 1. Placebo and low dose ZPL389 followed by 30mg ZPL389 (for subjects who received placebo 3mg or 10mg ZPL389 in the core study)
  - 2. Placebo and low dose ZPL389 followed by 50mg ZPL389 (for subjects who received placebo 3mg or 10mg ZPL389 in the core study)
  - 3. 30mg ZPL389 (for subjects who received 30mg ZPL389 in the core study)
  - 4. 50mg ZPL389 (for subjects who received 50mg ZPL389 in the core study)
- AEs with onset date after week 32 of study treatment. This summary will be based on the subset of the safety set comprising patients who have on study treatment data after week 32. By week 32 it is expected that the treatment received in the core study will have less direct influence and therefore treatment groups for this summary are
  - 1. 30mg ZPL389
  - 2. 50mg ZPL389

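### The SAP's three AE periods miss some treatment-emergent events that start after the last dose: certainly in the placebo, 3 mg and 10 mg arms, possibly in the 30 mg and 50 mg arms

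*SAP*

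**What the plan says.** SAP 2.7.1 restricts AE presentation to treatment-emergent events and closes the window with this rule: "AEs observed four weeks or more after last study treatment intake will not be considered as treatment-emergent". The aim of the split is stated too: "Thus AEs will be summarized for different time periods to cover the core and extension studies". The periods are:

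- **Period 1:** "AEs with onset date during the first 16 weeks of treatment where treatment group is the treatment group in the core study". The population is the whole safety set.
- **Period 2:** "AEs with onset date after week 16 but before week 32 of study treatment". Entry to this period is restricted as follows: "This summary will be based on the subset of the safety set comprised of patients who have on study treatment data after week 16". The four groups are placebo or low dose followed by 30 mg, placebo or low dose followed by 50 mg, patients on 30 mg in the core study, and patients on 50 mg in the core study.
- **Period 3:** onsets after week 32. Entry is restricted in the same way: "This summary will be based on the subset of the safety set comprising patients who have on study treatment data after week 32". The groups are 30 mg and 50 mg.

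The section then sets the table content (any AE, system organ class, preferred term, severity, relatedness). It adds summaries of serious events, deaths and events leading to discontinuation without tying them to a period. It names no overall AE table and no AE table for follow-up.

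Off-treatment time is part of the design. Protocol 3.1 and SAP 1.1 send patients who do not enter the extension into a 4-week treatment-free follow-up. Protocol 5.6.2 keeps early discontinuers in the visit schedule. Protocol 7.1 collects AEs to the end of study visit. Protocol 9.5.2 summarizes treatment-emergent AEs by treatment group with no period cut.

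**The concern.** The definition of what counts and the definition of where it is counted do not match. An event can be treatment-emergent because it starts within four weeks of the last dose, yet start too late for Period 1 and occur in a patient whom Period 2 does not admit. Followed exactly, the plan collects such an event, classes it as treatment-emergent and shows it in none of the general AE tables.

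Frequency of AEs is a core secondary endpoint that SAP Table 1-1 keeps in the report. Nor is the uncovered time free of drug. Protocol 3.3 gives a terminal half-life of 70 to 100 hours, so five half-lives are 5 x 70 / 24 = 14.6 to 5 x 100 / 24 = 20.8 days after the last dose.

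**Working it through.** The plan gives no figure to reproduce; this is a check of classification rules by study day.

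**Inputs**
- L = study day of last dose. Planned core completion is L = 112, since Protocol Table 6-1 puts the Week 16 visit on Day 113, the day after dosing ends.
- Last treatment-emergent day = L + 27, because an onset 28 or more days after last intake is excluded (SAP 2.7.1).
- C = last day of the period. SAP 2.7.1 gives no cut day. Assumption: C = 16 x 7 = 112 and C = 32 x 7 = 224. Taking Day 113 as the week-16 cut would change the counts by one day.

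**Formula.** For a patient with no dose after C (L at or below C), uncovered days = max(0, L + 27 - C).

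**Week 16, C = 112**

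| Last dose day | Calculation | Uncovered days |
|---|---|---|
| 85 | 85 + 27 - 112 | 0 |
| 86 | 86 + 27 - 112 | 1 (Day 113) |
| 90 | 90 + 27 - 112 | 5 (Days 113-117) |
| 100 | 100 + 27 - 112 | 15 (Days 113-127) |
| 105 | 105 + 27 - 112 | 20 (Days 113-132) |
| 112 | 112 + 27 - 112 | 27 (Days 113-139) |

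All these days fall before the Week 20 visit on Day 141, so the events would be collected.

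**Week 32, C = 224.** L = 197 gives 0; L = 198 gives 1; L = 210 gives 13; L = 224 gives 27 (Days 225-251).

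**Which arms**
- Placebo, 3 mg and 10 mg: Period 2 has a group for these patients only if they went on to 30 mg or 50 mg. A core-only patient has no column however the population is read, so the gap is certain.
- 30 mg and 50 mg: Period 2 has a group for them. Whether they qualify depends on the meaning of on-treatment data, which the SAP does not define. If it requires a dose after week 16, the gap applies. If it includes the four-week treatment-emergent window, they are counted in Period 2.
- After week 32 all patients have been on 30 mg or 50 mg, so the gap there depends on the same term.

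**Planned scale** (360 subjects from SAP section 3; 15% to 25% discontinuation and 202 to 230 extension subjects from SAP 1.1)
- 25% discontinuing: 360 x 0.75 = 270 completers; 270 - 202 = 68 not rolling over.
- 15% discontinuing: 360 x 0.85 = 306 completers; 306 - 230 = 76 not rolling over.
- Placebo, 3 mg and 10 mg make up 90 + 45 + 45 = 180 of 360. If roll-over were equal across arms (assumption), 34 to 38 of these completers would be in the arms where the gap is certain.

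Discontinuers with a last dose on Days 86 to 111 would add to this.

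**The case against.** **The wording may be looser than this reading.** If on-treatment data includes the four-week window, 30 mg and 50 mg patients are covered. That stands as a limit on scope, but does not help the other three arms, which have no column.

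**The period split is justified.** Two studies share one report, and placebo and low-dose patients were re-randomized in the extension, so SAP 2.7.1 has good reason to split by period. True; the gap lies in the edges of the split. It may also be said that SAP section 4 does not list the departure from Protocol 9.5.2, but the SAP explains other changes where they occur (2.3.2, 2.6.2), so this is editorial.

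**Core-only patients are not forgotten.** SAP 2.1 says that listings are in general ordered by treatment sequence, with a core-only group for every arm. A reader might infer that these patients vanish from reporting; the SAP does not support that. However, no AE listing is named, and a listing would not fill a summary table.

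**The visit windows might set the cut.** One might take Day 127 or Day 267 from SAP Table 2-1. The SAP limits those windows: "The concept of assessment windows will be used for the data that is summarized by visit". AEs are assigned by onset date, so they do not apply.

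**Week 32 itself may seem to have no period**, since Period 2 stops before it and Period 3 starts after it. If it means 32 completed weeks, the two meet at one boundary and no day is lost. Stating the cut day settles this.

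**Conclusion.** The point holds and is minor. Some treatment-emergent AEs that start after the last dose have no place in the general AE summaries. For onsets after week 16 in patients with no later dose, this is certain for placebo, 3 mg and 10 mg; for 30 mg and 50 mg, and for onsets after week 32, it depends on how on-treatment data is defined. With a Day 112 cut, the gap is at most 27 days per patient and affects only last doses on Days 86 to 112. About 68 to 76 planned completers across all arms were not expected to roll over. The actual number of patients and events cannot be had from the documents, because the trial stopped early.

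Two stronger inferences are not supported. A reader might infer a biased safety comparison with placebo. Period 1 applies one onset rule to every arm of the full safety set, so the 16-week table stays valid and no between-arm bias is claimed. A reader might also infer that serious events are lost. The summaries of serious events, deaths and discontinuations, and the QTc and liver outputs, are not expressly tied to the periods and may be unaffected.

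**What to change.** Keep the three periods and the 16-week table. Add one rule keyed to last dose, not to extension entry: SAP 2.2 defines the extension set by a visit, so a patient with an extension visit but no later dose would slip through a rule based on entry.

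Under the rule, any treatment-emergent AE with onset after a period's cut, in a patient with no dose after that cut, is counted once by last treatment received, including placebo, 3 mg and 10 mg. SAP 2.4.2 already uses last treatment for follow-up medications. Show these events in either of two ways:

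- one added follow-up summary (any AE, system organ class, preferred term); or
- a separately shown off-treatment row with the period of last dose.

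State the cut days used, for example Day 112 and Day 224, and define on-treatment data so that 30 mg and 50 mg patients are counted in one place only. Protocol 5.5.4 asks sites to "ensure that the Week 16 visit is scheduled such that the subjects take approximately 112 capsules in total", so some dosing may run slightly past Day 112. Say where a core-only patient in that position is counted, because placebo, 3 mg and 10 mg patients would still have no Period 2 group.

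The cost is a few lines of SAP text and a small amount of output; no new data are needed. The downside is that the added counts will be sparse and non-comparative.

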# 2.1.1 General definitions

Study treatment is either placebo or 3, 10, 30 or 50mg ZPL389.

Day 1 is defined to be the first day of administration of any study treatment.

All other study days will be labeled relative to Day 1. For event dates on or after Day 1, studyday for a particular event date is calculated as [Date of event] – [Date of first dose]+1, i.e., Day 2, Day 3, etc., will be one day, two days, etc., after Day 1, respectively. For the dates beforeDay 1, study day for an event date is calculated as [Date of event] – [Date of first dose], i.e., Day - 1, Day -2, etc., will be one day, two days, etc., before Day 1, respectively. Duration of an event will be calculated as (Event end date – Event start date + 1).

The descriptor "Day 0" will not be used.

Screening refers to any procedure (e.g., checking inclusion and exclusion criteria) performed prior to the date of first dose of study treatment. Per protocol, subject informed consent must be obtained prior to performing any study related activity. The date of signing informed consent is the start date of screening period.

Baseline is considered to be the last assessment (including those from unscheduled visits) obtained before the first dose of study treatment. All assessments obtained after first dose of study treatment are considered as post-baseline unless otherwise specified.

In general, a baseline value refers to the last measurement made prior to administration of the first dose of study treatment. However, if no pre-treatment value exists, values obtained after first dose of treatment but on that same day of dosing will be considered as the baseline.

The date of last dose will be collected via the CRF. The end of the treatment period will be defined as the last dose date or last visit in treatment period whichever occurs earlier. i.e., for subjects who discontinued or have their last visit earlier than last dose date, the end of study treatment will be the date of the last study visit in the corresponding treatment period.

The core study treatment period is defined to be the time up until the date of the first visit in the extension study whilst the patient is receiving study treatment.

The extension study treatment period is defined to be the time up from the first visit in the extension study until the end of study treatment

The follow-up period is defined to be the time from last dose of study treatment until the end of the study (latest of core and extension for that patient).

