#### Concomitant medication

Concomitant medications are defined as drugs taken at least once between start and end of study treatment (inclusive)

Concomitant treatments will be displayed for:

- the core study treatment period by the relevant treatment group for that period,
- the extension study treatment period by the relevant treatment group for that period

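### The SAP splits adverse events at 16 weeks from first dose, not at the actual change of treatment, so off-schedule switchers have some events shown against a treatment they were not taking at onset

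*SAP*

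**What the plan says.** SAP 2.7.1 gives the purpose of the adverse event tables as "to understand what AEs are reported within different time periods relative to start of treatment". It plans three tables.

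- The first covers "AEs with onset date during the first 16 weeks of treatment where treatment group is the treatment group in the core study".
- The second covers "AEs with onset date after week 16 but before week 32 of study treatment" and has four columns. Two are sequence columns for patients who change treatment, for example "Placebo and low dose ZPL389 followed by 30mg ZPL389 (for subjects who received placebo 3mg or 10mg ZPL389 in the core study". The other two are for patients on 30 mg or 50 mg in both studies.
- The third covers onset after Week 32 and has plain 30 mg and 50 mg columns. The reason given is that "By week 32 it is expected that the treatment received in the core study will have less direct influence".

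SAP 2.1.1 defines treatment periods in another way: "The core study treatment period is defined to be the time up until the date of the first visit in the extension study". The concomitant medication part of SAP 2.4.2 uses these periods and reports "the extension study treatment period by the relevant treatment group for that period".

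Under SAP 1.1, patients on core placebo, 3 mg or 10 mg are randomized 1:1 to 30 mg or 50 mg when they enter the extension. Patients on 30 mg or 50 mg keep their dose. SAP Table 1-2 makes adverse event frequency at Weeks 32 and 116 the primary endpoint of the extension.

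**The concern.** For a placebo, 3 mg or 10 mg patient, treatment changes at entry to the extension, not at a fixed number of weeks. The planned Week 16 visit is Day 113, the day after the last core dose (Protocol Table 6-1, footnote 1), but it can move. Protocol 5.5.4 tells sites to "ensure that the Week 16 visit is scheduled such that the subjects take approximately 112 capsules in total". Protocol Section 6 asks only that visits be as near the designated day as possible. SAP Table 2-1 accepts Days 100 to 127 as Week 16. SAP 2.3.1 notes that part of the study ran during the COVID-19 pandemic, which makes off-schedule visits plausible.

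Take a placebo patient who starts extension treatment on Day 120 and has an event on Day 118. The event began on placebo, yet it is shown in a column that a reader will take to describe the time after the change to 30 mg or 50 mg. The reverse happens when the change is early. These tables serve the extension's primary endpoint, and the two sequence columns are the ones that show first exposure to 30 mg or 50 mg. The SAP also uses a different boundary for concomitant medication in the same patients.

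**Working it through.** **Inputs.** Scheduled days 113 (Week 16) and 225 (Week 32), and the Week 16 window of Days 100 to 127, come from SAP Table 2-1. The planned extension size of 202 to 230 comes from SAP 1.1. The core allocation of 90:45:45:90:90 comes from Protocol 9.8.

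**Plan's own days.** 7 × 16 + 1 = 113 and 7 × 32 + 1 = 225, as in Table 2-1. Counted from first dose, the first table therefore covers Days 1 to 112 and the second Days 113 to 224, which is 112 days each. SAP 2.7.1 does not state study days, so Day 112 is inferred from 16 × 7.

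**Misplaced time.** Let s be the day of the first extension dose.

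- Late switch (s > 113): s − 113 days of the second period are before extension treatment. The share is (s − 113)/112.
- Early switch (s < 113): 113 − s days of the first period are on 30 mg or 50 mg. The share is (113 − s)/112.

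| Switch day | Misplaced days | Share of that patient's period |
|---|---|---|
| 113 (planned) | 0 | 0% |
| 116 | 3 late | 3/112 = 2.7% |
| 120 | 7 late | 7/112 = 6.3% |
| 127 (window edge) | 14 late | 14/112 = 12.5% |
| 110 | 3 early | 3/112 = 2.7% |
| 106 | 7 early | 7/112 = 6.3% |
| 100 (window edge) | 13 early | 13/112 = 11.6% |

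**Patients exposed to the problem.** (90 + 45 + 45)/360 = 50% of planned core patients would change treatment. If roll-over is equal across arms (assumption), that is 101 to 115 of the 202 to 230 planned entrants. The early stop makes the real number smaller.

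**Events.** Assume that 20% to 40% of patients have an event in 112 days, at a constant rate. The chance of at least one onset in d misplaced days is 1 − (1 − r)^(d/112).

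- d = 7: 1.4% (r = 0.20) to 3.1% (r = 0.40)
- d = 14: 2.8% to 6.2%

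These are percentages of the delayed patients only. Even if every switcher were 14 days late, a sequence column's any-event percentage could rise by no more than 2.8 to 6.2 points. The true rise would be smaller, because some of these patients would have another event in the column anyway.

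**Patients who do not enter the extension.** SAP 2.7.1 counts events as treatment-emergent until four weeks after last intake. With a last dose on Day 112, the treatment-emergent time after Week 16 runs from Day 113 to Day 139, which is 27 days. These events are too late for the first table. The second table is limited to patients with on-treatment data after Week 16, and it has no column for a placebo, 3 mg or 10 mg patient who did not go on to 30 mg or 50 mg.

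**The case against.** The fixed clock is deliberate. SAP 2.7.1 says that the periods run from start of treatment, and SAP Table 1-2 states the extension objective in total weeks of treatment (32 and 116), counted from the core study. The section also treats 16 weeks and core treatment as nearly the same thing, so a programmer might take Week 16 to mean the end of core treatment, and then nothing is misplaced. The tables are descriptive. Both studies were stopped for lack of efficacy, and listings are in general by full treatment sequence (SAP 2.1), so events near the switch can be examined one by one.

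Much of this stands. The clock is a legitimate choice for the Week 32 cut, no test depends on these tables, and no decision will change. But a clock says when an event began, while the columns say under which treatment, and for an off-schedule switcher the two disagree. If the end of core treatment was meant, the SAP should say so.

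A reader might infer that placebo and low-dose events are counted as 30 mg or 50 mg events. The documents do not support that. Switchers have their own columns, whose labels name the placebo or low-dose phase first. The columns for 30 mg or 50 mg throughout contain no switchers, and plain dose columns appear only after Week 32. A reader might also take Protocol 5.5.4 to delay the visit by one day per missed dose. It asks only for an approximate capsule total, so missed doses cannot be converted into switch days.

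**Conclusion.** The point holds as a minor one. Read as written, SAP 2.7.1 places some events of off-schedule switchers against a treatment not being taken at onset, in either direction, although the SAP has a switch-based period and uses it for concomitant medication. Nothing is misplaced for a switch on Day 113. At the edges of the SAP's Week 16 window the misplaced share is 11.6% (early) or 12.5% (late) of one patient's period.

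This rests on reading Week 16 as Day 112, and on using the analysis window as a guide to how far the switch can move. The window does not limit when visits happen. The documents do not give the actual switch days, and the extension's visit and dosing rules are in a separate protocol that was not available. The size can therefore be given only as a range per patient. The event percentages also rest on the assumed 20% to 40% event rate.

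**What to change.** In SAP 2.7.1:

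1. For patients who enter the extension, end the core table the day before the first extension dose, and start the second table at the first extension dose. Keep the four sequence columns and the Week 32 cut.
2. For patients who do not enter, keep the 16-week limit in the core table. Show their treatment-emergent events after Week 16, up to the four-week limit after last dose, in a separate summary by core arm. Adding this time to the core table instead would lengthen the window by up to 27/112 = 24% for non-entrants only, so window length would depend on roll-over.
3. State the exposure time in each column.

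The cost is small: one changed derivation and one extra summary, with no new data if first extension dose dates are recorded. The downside is that period lengths vary between entrants. For switches between Day 100 and Day 127, the core period would run from 99 to 126 days, and the second period from 125 (Days 100 to 224) down to 98 (Days 127 to 224), against 112 for each now. Item 3 makes this visible. If the fixed cut is kept, the SAP should at least state how events between Week 16 and the switch are assigned, and how events after an early switch are assigned.
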